### 7.2.3 EXPECTEDNESS

Reported events will be categorized as Expected Treatment Effects if the event meets the definition of any typical treatment side-effect of study devices of mild to moderate severity and lasting up to a typical maximum duration.

## 7.3 TIME PERIOD AND FREQUENCY FOR EVENT ASSESSMENT AND FOLLOW-UP

The occurrence of an AE or SAE may come to the attention of study personnel during a study visit or upon review by a study monitor. All ETEs and AEs will be captured on the appropriate data form. Information to be collected includes event description, date of onset, clinician's assessment of seriousness and severity, relationship to study device/treatment (assessed only by those with the training and authority to make a determination), actions taken, and date of event resolution. All AEs occurring while on study must be documented appropriately regardless of relationship. All ETEs/AEs assessed as "not yet resolved" must continue to be followed via telephone contact, by email, or clinic visit every 7 days or sooner (as per the physician's direction until event resolution or stabilization or tissue resection).

A pre-existing condition should not be reported as an adverse event unless there has been a substantial increase in severity or frequency of the problem that has not been attributed to natural history.

Changes in the severity of an event will be documented to allow for a determination if the event should be re-categorized from an ETE to AE.

The PI will record all reportable events, with start dates, occurring any time after informed consent is obtained until seven days (for non-serious AEs) or 30 days (for SAEs) after the last day of study participation. At each study visit, the investigator will inquire about the occurrence of ETEs/AEs/SAEs since the last visit. Events will be followed for

outcome information until resolution or stabilization.

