#### 2.1.2 BRIEF SKIN CONDITION BACKGROUND AND TREATMENT OVERVIEW

The Mosaic Ultra can potentially treat skin tone and texture, facial rejuvenation, photoaging, wrinkles, scars, stretch marks, acne vulgaris and hair loss.

Pigmented lesions refer to a wide range of abnormalities that can be found on the skin, including not limited to lentigos (age spots), solar lentigos (sunspots), and ephelides (freckles). Many people develop brown lesions on their skin from chronic sun exposure, time, and other factors. These can appear on the face, hands, upper chest, and other locations and tend to make the skin look prematurely aged.

Uneven skin tone and skin texture can occur naturally over time as the skin is exposed to UV rays from the sun. This exposure causes the skin to produce melanin which results in the skin having dark spots resulting in the uneven tone.

This same exposure can cause a breakdown of the skin's natural collagen and elastin which typically support healthy skin. As the collagen and elastin breaks down it can cause the skin to dry out and become rougher resulting in an undesired skin texture.

Wrinkling occurs due to a variety of factors but results in the skin folding into itself and instead of appearing smooth the skin has folds, ridges, and creases. Wrinkles can occur as part of the natural ageing process, exposure to the sun, and a large variety of lifestyle and health habits.

Scars are marks on the skin that are left after the body heals from a wound and are typically a sign that the skin did not heal uniformly. Scars can occur due to a variety of wounds such as (but not limited to) acne inflammation, accidental injuries and cut and burns.

Stretch marks, also known as striae, occur when the skin has been rapidly stretched. The most common cause of stretch marks are pregnancy, but they can also occur if a person gains or loses weight in a short period of time. Stretch marks are typically smaller indented streaks and lines on the skin that can come in many colors such as pink, red, black, blue or purple.

Acne vulgaris is a very common skin issue that is a result of hair follicles under the skin becoming plugged or clogged. It results in small red bumps on the skin which can be painful to some patients due to the inflammation of the hair follicles.

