### 4.3.2 SECONDARY ENDPOINTS

The secondary endpoints of this clinical trial include:

1. Subject satisfaction
2. Physician satisfaction

Table 3: Satisfaction Scale

Score	Rating
6	Extremely Satisfied
5	Satisfied
4	Slightly Satisfied
3	Slightly Dissatisfied
2	Dissatisfied
1	Extremely Dissatisfied

3. Physician CGAIS

4. Subject CGAIS

Table 4: Clinical Global Aesthetic Improvement Scale

Score	Rating	Description
5	Very Much Improved	Optimal cosmetic result in the subject
4	Much Improved	Marked improvement in appearance from the initial condition, but not completely optimal
3	Improved	Obvious improvement in appearance from initial condition, but further treatments may be beneficial
2	No Change	The appearance is essentially the same as the original condition
1	Worsened	The appearance is worse than the original condition

5. Adverse event assessment

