### **7. ASSESSMENT OF SAFETY**

#### **7.1 SPECIFICATIONS OF SAFETY PARAMETERS**

### 7.1.1 DEFINITION OF AN EXPECTED TREATMENT EFFECT (ETE) AND AN ADVERSE EVENT (AE)

An expected treatment effect is defined as any typical treatment side-effect of the study devices of mild to moderate severity and lasting up to a typical maximum duration. An adverse event is defined as any new medical problem, or exacerbation of an existing problem, experienced by a participant while enrolled in the study, whether or not it is considered device-related by the investigator. All ETEs and AEs will be collected during the conduct of this trial.

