## 7.4 REPORTING PROCEDURES

### 7.4.1 ADVERSE EVENT REPORTING

Any new medical problem, or an exacerbation of an existing condition, reported from the time the informed consent form is signed must be followed until the last study visit after the last study treatment/exposure or until event resolution.

AEs will not be followed up after the final study visit.

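### Section 7.3 keeps worsening of a pre-existing condition out of the adverse event record when it is put down to natural history, which conflicts with the definition in 7.1.1 and reaches the conditions treated in Group A

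*Combined protocol and SAP*

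**What the plan says.** - **Section 7.1.1 (definition).** An AE includes "exacerbation of an existing problem, experienced by a participant while enrolled in the study, whether or not it is considered device-related by the investigator". It sets no severity threshold. It adds: "All ETEs and AEs will be collected during the conduct of this trial".
- **Section 7.3 (event assessment and follow-up).** A pre-existing condition is not to be reported as an AE "unless there has been a substantial increase in severity or frequency of the problem that has not been attributed to natural history". The same section also states: "All AEs occurring while on study must be documented appropriately regardless of relationship".
- **Section 7.4.1 (AE reporting).** It opens as follows: "Any new medical problem, or an exacerbation of an existing condition, reported from the time the informed consent form is signed must be followed". Follow-up then runs to the final visit or to resolution. The section contains neither of the two conditions in 7.3.
- **Section 7.2.2 (relationship).** Five categories run from definite to unrelated. The lower two cover events with no reasonable causal link to the device.
- **Section 2.1.2 (conditions treated).** "The Mosaic Ultra can potentially treat skin tone and texture, facial rejuvenation, photoaging, wrinkles, scars, stretch marks, acne vulgaris and hair loss".
- **Section 4.3.2, Table 4.** CGAIS score 1 (Worsened) is described as: "The appearance is worse than the original condition". It is a secondary endpoint and is not linked to AE reporting.
- **Section 4.4.** An acceptable AE and side-effect profile is the second of the two Group A success criteria. No numeric limit is given.

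**The concern.** A clause that leaves stable comorbidities off the AE form is common and usually harmless. Here the device is aimed at the pre-existing conditions themselves, so the clause applies to the treated skin or scalp. If a treated scar thickens or treated acne flares, device effect and natural course are competing explanations. Section 7.3 lets the choice between them decide whether an AE record exists at all.

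Three things depend on that record: AE assessment as a secondary endpoint, Group A success criterion 2, and the sponsor's ability to stop the study on AE incidence (Section 5.5). With three sites planned in the synopsis and Section 4.1, two investigators could handle the same event differently, each following a section of the protocol. An event that was never recorded may not be recoverable at analysis.

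**Working it through.** No figure in the plan bears on this point, so the check compares the sections case by case.

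| State of a pre-existing condition after treatment | Section 7.1.1 | Section 7.3 |
|---|---|---|
| Unchanged | Not an AE | Not reported |
| Worse, but not substantially | AE, as an exacerbation | Not reported |
| Substantially worse, attributed to natural history | AE, attribution irrelevant | Not reported |
| Substantially worse, not so attributed | AE | Reported |

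The sections disagree in two of the three cases of worsening, and the two disagreements differ in strength.

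1. **Substantial worsening attributed to natural history: a hard conflict.** Section 7.1.1 makes the presumed cause irrelevant to whether the event is an AE, and 7.3 makes it decisive. No reading satisfies both.
2. **Non-substantial worsening: a softer conflict.** The word substantial could be meant to explain what counts as an exacerbation. It is not defined, however, so investigators have no common threshold.

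**Who makes the attribution.** Section 7.3 restricts the device-relationship assessment to people with the training and authority to make it. It names nobody for the natural-history attribution, although that is also a causal judgement and comes earlier.

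**Whether the exception reaches the treated area.** The conditions in Section 2.1.2 are mostly present at entry. The shorter list in Section 3 (lesions, periorbital wrinkles, acne scars and surgical scars) is too. Nothing exempts the treated condition from the 7.3 rule.

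**Whether the attribution can be tested.** The study is non-randomized and both groups are treated, so there is no untreated group to show the natural course.

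**What else would capture the worsening.** In the Group A schedule (Table 5), subject and physician evaluations fall only at the 30- and 90-day visits after the final treatment. Photographs are scheduled at the treatment visits as well. A participant who worsens during a course of up to 5 treatments and leaves has no scheduled CGAIS. Under Section 9.1 that participant is excluded from the efficacy analysis but kept in the safety analysis, so the AE record matters most there.

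**The case against.** The case against giving this much weight is substantial, and most of it stands.

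- **General and specific rule.** The 7.3 sentence may be meant to refine 7.1.1, and the instruction to document AEs whatever their relationship may apply only to events that already qualify. That is a fair reading of the threshold. It does not rescue the natural-history clause, because a refinement cannot reverse a definition that disregards cause.
- **Section 7.4.1.** A reader might infer that it repeats the 7.1.1 rule. It does not: it has no relatedness clause and governs how long reported problems are followed. It is a weaker inconsistency.
- **Most listed device harms are new events.** Burns, blistering, infection, prolonged redness and bruising (Section 2.3.1) are new problems, which 7.3 does not exclude. The overlap with treated conditions is limited, for example to thickened scars, discoloration or textural change. Section 2.3.1 does not list worsening of the treated condition as such.
- **The harm is not hidden.** CGAIS is scored separately by subject and physician, and the subject's score does not depend on the investigator's attribution. Section 9.3 requires counts and frequencies of categorical results. This holds for participants who reach day 30 or 90. CGAIS remains a secondary endpoint and not an AE record.
- **A tempting quantification fails.** A reader might assume that 1% to 10% of the 180 Group A participants worsen (0.01 × 180 = 1.8 to 0.10 × 180 = 18) and set 2 to 18 AEs under 7.1.1 against none under 7.3. The documents give no basis for that range. A CGAIS score of 1 rates appearance and is not automatically an exacerbation. Where a new burn or new hyperpigmentation caused it, the event is reportable under both sections. Zero is only a worst case.
- **Effect on conclusions.** Criterion 2 has no numeric limit, so no recount would mechanically change success. The image-selection primary endpoint is untouched.

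**Conclusion.** The inconsistency is real. Sections 7.1.1 and 7.3 cannot both be followed when a pre-existing condition worsens substantially and the worsening is attributed to natural history. They also leave smaller worsening to an undefined threshold. Because the Group A targets are pre-existing and there is no untreated arm, worsening in the treated area can be left out of the AE profile by an attribution made before recording and not testable within the study.

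The size is unknown. It depends on how often treated conditions worsen, how often investigators invoke natural history, and which section sites follow. The documents do not support the stronger inferences that such worsening would go wholly unseen or that a particular number of AEs would be lost.

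This is a correction worth making to the definition behind the safety counts. It does not invalidate the design of this pilot study, and I would rank it below the defects that must be resolved before the study can be relied on.

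**What to change.** Reconcile 7.3 with 7.1.1 and state which section governs. In substance, 7.3 should say:

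- An unchanged pre-existing condition is not an AE.
- Any worsening of a pre-existing condition in the treated area is recorded as an AE, whatever its presumed cause.
- Presumed natural history is entered only in the relationship field, using the existing categories in Section 7.2.2.

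If the sponsor wants a threshold for conditions outside the treated area, substantial should be defined and 7.1.1 amended to match. Section 7.4.1 should then use the same terms.

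As an optional safeguard, a CGAIS score of 1 from subject or physician with no AE record may prompt a data query. It should not create an AE automatically, since the scale rates appearance.

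The cost is a short text amendment and, if wanted, one edit check. The downside is that the reported AE rate may become slightly less favourable, partly through events later judged unrelated. The relationship field lets those be shown separately.

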## 7.4 REPORTING PROCEDURES

### 7.4.1 ADVERSE EVENT REPORTING

Any new medical problem, or an exacerbation of an existing condition, reported from the time the informed consent form is signed must be followed until the last study visit after the last study treatment/exposure or until event resolution.

AEs will not be followed up after the final study visit.

### 7.4.2 SERIOUS ADVERSE EVENT REPORTING

Serious adverse events must be reported to the Sponsor as soon as possible, preferably within 24 hours but in no event later than 72 hours. Any AE considered serious by the PI or Sub-investigator, or which meets the definition of an SAE included in **Section 7.1.2. Definition of Serious Adverse Event** must be documented on an SAE data form.

The Sponsor will conduct an investigation. If the Sponsor determines that the investigation presents an unreasonable risk to participants, all investigations or parts of the investigation presenting that risk will be terminated as soon as possible. The investigator must report serious adverse events to the reviewing IRB according to the IRB regulations at the study site.

### 7.4.3 UNANTICIPATED ADVERSE DEVICE EFFECT REPORTING

If an unanticipated adverse device effect occurs, the study investigator shall complete the appropriate study-specific data form, and submit to the study sponsor and to the reviewing IRB as soon as possible, but in no event later than 10 working days after the investigator first learns of the effect. The study sponsor contact information is provided in **Section 1. Key Roles**. The study sponsor is responsible for conducting an evaluation of an unanticipated adverse device effect and shall report the results of such evaluation to FDA and to all reviewing IRBs and participating investigators within 10 working days after the sponsor first receives notice of the effect. Thereafter the sponsor shall submit such additional reports concerning the effect (as FDA requests).

### 7.4.4 REPORTING OF PREGNANCY

Each pregnancy that starts during the participant's study participation must be reported by the investigator to the Sponsor within 24 hours of learning of its occurrence. Pregnancies and pregnancy follow-up should be reported on an Adverse Event form. Pregnancy follow-up should describe the outcome of the pregnancy, including any voluntary or spontaneous discontinuation; details of the birth; the presence or absence of any congenital abnormalities, birth defects, maternal or newborn complications, and their relationship to the device or treatment/exposure. Each pregnancy must be reported as a non-serious AE if the participant has received at least one study treatment/exposure. The following criteria should be followed:

- a. If a participant becomes pregnant after the Baseline visit and all study treatments/test spot exposure have been completed, the participant should continue to be followed for the duration of the pregnancy.
- b. If a participant becomes pregnant after the Baseline visit but before any study treatments/test spot exposures, the participant should be exited from the study.

- c. If a participant becomes pregnant after the Baseline visit but before all study treatments/test spot exposures have been completed, additional study treatments/test spot exposures should be discontinued and the participant should continue to be followed for the duration of the pregnancy.

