### 7.1.2 DEFINITION OF SERIOUS ADVERSE EVENT (SAE)

Each adverse event should be assessed for its seriousness. The definition below should be used for this assessment. Please note that the term serious adverse event is not synonymous with a “severe” adverse event, which may be used to describe the intensity of an event experienced by the participant.

An adverse event should be classified as serious if it meets any of the following criteria:

- a. Death  
Death was an outcome of the adverse event.
- b. Life-threatening  
The participant was at substantial risk of dying at the time of the adverse event or use or continued use of the device.
- c. Hospitalization (initial or prolonged)  
Admission to the hospital or prolongation of hospitalization was a result of the adverse event.
- d. Disability or Permanent Damage  
The adverse event resulted in a substantial disruption of a person's ability to conduct normal life functions (ie, the adverse event resulted in a significant, persistent or permanent change, impairment, damage or disruption in the patient's body function/structure, physical activities and/or quality of life).
- e. Congenital Anomaly/Birth Defect  
Exposure to a medical product prior to conception or during pregnancy may have resulted in an adverse outcome in the child.
- f. Required Intervention to Prevent Permanent Impairment or Damage (Devices)  
Medical or surgical intervention was necessary to preclude permanent impairment of a body function, or prevent permanent damage to a body structure (either situation suspected to be due to the use of a medical product).
- g. Other Serious (Important Medical Events)  
The event does not fit the other outcomes, but the event may jeopardize the participant and may require medical or surgical intervention (treatment) to prevent one of the other outcomes.

Non-serious adverse events are all events that do not meet the criteria for a “serious” adverse event.

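### Section 7.4.4 labels every post-exposure pregnancy non-serious and sends its outcome to the AE form, with no link to the SAE rules in 7.1.2 and 7.4.2, so a serious outcome can be routed either way

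*Combined protocol and SAP*

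**What the plan says.** All references are to the combined protocol and SAP.

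- **7.4.4 (pregnancy).** A pregnancy that starts on study "must be reported by the investigator to the Sponsor within 24 hours of learning of its occurrence". On classification: "Each pregnancy must be reported as a non-serious AE if the participant has received at least one study treatment/exposure". On the form: "Pregnancies and pregnancy follow-up should be reported on an Adverse Event form". The follow-up is to describe, among other things, "the presence or absence of any congenital abnormalities, birth defects, maternal or newborn complications, and their relationship to the device or treatment/exposure". Exposed participants are followed to the end of the pregnancy. The section gives no reporting time for the outcome and does not mention 7.1.2 or 7.4.2.
- **7.1.2 (seriousness).** One criterion is enough to make an adverse event serious. Criterion (c), hospitalization, reads: "Admission to the hospital or prolongation of hospitalization was a result of the adverse event". Criterion (e), congenital anomaly or birth defect, reads: "Exposure to a medical product prior to conception or during pregnancy may have resulted in an adverse outcome in the child". Events that meet no criterion are non-serious, so the two classes exclude each other.
- **7.4.2 (SAE reporting).** Any AE that the investigator or sub-investigator considers serious, or that meets 7.1.2, "must be documented on an SAE data form". It must reach the sponsor preferably within 24 hours and at the latest within 72. The sponsor then investigates, and the investigator reports to the IRB.
- **7.3 and 7.4.1 (time limits).** Recording stops 7 days (non-serious AEs) or 30 days (SAEs) after the last day of participation. Section 7.4.1 adds that AEs are not followed beyond the final visit.

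**The concern.** The instruction in 7.4.4 is unconditional. It fixes the class before the outcome is known, and it names birth defects and complications as content for the AE form. Those are outcomes that 7.1.2 can make serious and that 7.4.2 would send to another form with a deadline. No section says which rule prevails, or that a serious outcome is a separate event from the pregnancy.

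Much hangs on the route. SAE status brings the 24 to 72 hour report, the sponsor's investigation and the IRB report; the AE form alone brings none of these. Adverse event assessment is also a secondary endpoint (4.3.2), and an acceptable adverse event profile is a Group A success criterion (4.4). How such a case is presented would depend on which section the site had open.

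**Working it through.** The plan states no figure on this point, so the first check sets the rules side by side.

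| Event after at least one exposure | Under 7.4.4 | Under 7.1.2 and 7.4.2 |
|---|---|---|
| Pregnancy loss with a hospital admission that results from it | Part of pregnancy follow-up; AE form; pregnancy labelled non-serious | Serious by (c); SAE form; at most 72 hours |
| Birth defect that exposure may have caused | Part of pregnancy follow-up; AE form | Serious by (e); SAE form; at most 72 hours |
| Uncomplicated birth in hospital | Pregnancy labelled non-serious | Fits the words of (c), since the pregnancy is itself the AE and no exception is made for delivery |

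In the first two rows both class and form can differ. In the third there is no second event to carry the serious label, so the conflict falls on the pregnancy record itself. Whether that row arises in practice depends on the recording window.

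**When does the SAE window in 7.3 close?** Inputs: the last Group A visit is 90 ± 14 days after the final treatment (6.4); the last Group B visit is no later than day 90 after its single treatment (Table 5, 6.4); the SAE window is 30 days after the last day of participation (7.3). I assume that participation ends at the last scheduled visit and that term is about 38 weeks from conception, 38 × 7 = 266 days.

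- Group A: 90 + 14 + 30 = 134 days after the final treatment.
- Group B: 90 + 30 = 120 days after treatment.
- Conception on the day of the last treatment: term birth at about day 266, which is 266 − 134 = 132 days (A) or 266 − 120 = 146 days (B) after the window closes.

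A later conception moves the birth later still. For a term birth to fall inside the window, conception would have to precede the last treatment by at least 132 days (A) or 146 days (B). Pregnancy tests are scheduled at screening and at treatment visits (Table 5), and treatment stops on pregnancy (5.4, 7.4.4), so this is implausible.

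Two consequences follow:

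1. A birth defect found at term will usually arise after the ordinary SAE window. The 7.4.4 follow-up on the AE form may then be the only route by which it arrives, and that route has no clock for the outcome.
2. An early loss with admission can fall well inside the window. With conception on the day of the last Group A treatment, 134 days is 134 / 7 ≈ 19 weeks. For such a case both rules are in force at once.

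**The case against.** The best defence is that the sections can be read together. The pregnancy is one non-serious AE; a serious outcome is a separate event, caught by 7.4.2, which covers any AE meeting 7.1.2 and makes no carve-out for pregnancy. Section 7.3 has the clinician's assessment of seriousness collected for events, so using the AE form does not in itself cancel the 7.4.2 duty. The sponsor has also been told of the pregnancy within 24 hours. On this view the defect is a missing cross-reference.

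Much of that stands. Misrouting is possible, not inevitable. But the joint reading is nowhere stated, and 7.4.4, the more specific section, points the other way by listing birth defects and complications as follow-up content for the AE form. Knowing of a pregnancy is not the same as receiving its outcome on time.

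It is also fair that an uncomplicated term delivery mostly falls outside the ordinary SAE window. It becomes an issue only if following the pregnancy to its end, or following an open event to resolution under 7.3, is taken to extend that window. The documents do not settle this, and 7.4.1 pulls the other way.

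Finally, the Group A safety criterion has no numerical threshold, so no count decides it.

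**Conclusion.** The point holds as an unreconciled conflict in safety classification and routing. Under the text as written, a pregnancy outcome that meets 7.1.2 can be handled under 7.4.4 or under 7.4.2, and the first route lacks the SAE deadline, the sponsor's investigation and the IRB report. It should be corrected because a stated rule can misdirect a serious outcome. Its reach is limited to safety reporting; the primary endpoint and the sample size are unaffected. The timing argument rests on the 266-day assumption and on participation ending at the last scheduled visit. The textual conflict rests on neither.

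A reader might infer more, without support in the documents:

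- *That one pregnancy is counted both ways.* There is no tabulation rule for pregnancies, so the text shows that a case can be classified either way, not that it is counted twice.
- *That every admission or birth defect is serious.* Criterion (c) requires the admission to result from the event, and (e) concerns outcomes that exposure may have caused.
- *That several SAEs are at stake.* An assumed pregnancy rate of 1% to 3% of 210 gives 2.1 to 6.3 pregnancies. But the documents give no rate, the 210 include men and participants up to age 60, and each pregnancy would need a qualifying admission inside the window. No such estimate should be used.
- *That an uncomplicated pregnancy cannot be an AE because of 7.1.1* ("An adverse event is defined as any new medical problem, or exacerbation of an existing problem"). Section 7.4.4 is a specific rule that deems it one. That is a convention, as is the choice between the AE form and a separate pregnancy form.

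**What to change.** Reconcile 7.4.4 with 7.1.2, 7.3 and 7.4.2:

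1. In 7.4.4, confine the non-serious label to the pregnancy itself.
2. In 7.4.4, state that each outcome or complication (loss, congenital abnormality, maternal or newborn complication) is assessed as an event in its own right under 7.1.2. If serious, it goes on the SAE form within the 7.4.2 limits, counted from when the investigator learns of the outcome.
3. In 7.3, and by reference in 7.4.1, state that this duty continues after the ordinary recording window for any pregnancy being followed under 7.4.4.
4. In 7.1.2(c) or 7.4.4, state how an admission for delivery is classified, so that all sites treat it alike.

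The existing AE form can stay. The cost is a few sentences, an amendment under 13.2 and a short note to sites. The downside is a small amount of reporting after the final visit, on pregnancies that 7.4.4 already requires to be followed. Design, treatment and the efficacy analysis do not change.
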